Oral mucositis in advanced stages, similar to a FGG donor site, can be extremely painful, preventing a patient from eating and even disrupting the patient's daily functions. The aim of this study will be to compare patient-based outcomes, specifically postoperative pain, at the FGG donor sites, using an interventional parallel-group design, whereby a hemostatic gauze, Surgicel®, will be placed within all of the palatal donor sites and covered with either episil® (test) or a cyanoacrylate dressing, PeriAcryl®90 (control). The secondary aim of this study will be to compare gingival healing via measurement of the gingival blood flow at the FGG donor sites by the laser Doppler flowmetry (LDF) technique, by monitoring blood perfusion. The hypothesis for the present study is that patient-based outcomes and gingival blood flow will be more favorable for the FGG donor sites being covered by the test wound dressing material episil® compared to the control dressing.

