instructions for self-application as needed 3 times daily for pain relief. A sufficient supply of the episil® will be provided to the test subjects for the study duration. The total duration of the study per subject will be 21 days from the day of the surgical procedure. The primary outcome of postoperative pain will be determined by the subjects recording their postoperative pain threshold using a Visual Analog Scale Form/Questionnaire and the number of analgesic pills taken each day at 1, 2, 3, 5, 7, 10, 14 and 21 days postoperatively. The Visual Analog Scale Form/Questionnaire for post-operative days 1, 2, 5 and 10 will be completed at the subject's place of residence, while the Visual Analog Scale Form/Questionnaire for days 3, 7, 14 and 21 will be completed at the subject's post-operative appointments at the dental clinic. The Visual Analog Scale Form/Questionnaire will evaluate the subjects' postoperative pain using a visual analog scale (VAS) scores from 1 to 10, with 1 indicating minimal pain and 10 indicating severe pain. If no pain is present, a score of 0 will be given. The levels of postoperative pain will be classified as none to minimum if the score is "0 to 3," moderate for "4 to 6," and severe for "7 to 10." None to minimal pain will mean little or no discomfort; moderate is any pain that bothers the subject and mildly affects normal function; and severe will be considered any pain that will not be tolerated and may even disrupt the subject's daily functions.

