One of the secondary outcomes, gingival blood flow, will be determined with the laser Doppler flowmetry (LDF) technique to measure the blood perfusion of the FGG donor site and as well as the contralateral side of the palate, as a positive control, at baseline prior to surgery, immediately after harvesting of the FGG from donor site, and on post-operative days 3, 7, 14 and 21. The LDF technique is an unbiased non-invasive method of monitoring the response to periodontal therapy. It is adequate for recording changes in gingival blood flow following periodontal surgery presenting different patterns of microvascular blood flow alterations during the wound-healing period. The LDF technique is based on the Doppler principle. A laser beam will be emitted by an optical fibre onto the FGG donor site. The light hitting moving erythrocytes is scattered back in shifting frequency, which is the Doppler effect, and is captured by one or more optical fibers. The light signals are then converted into electric signals and the resulting photocurrent is processed to provide a recording of the blood flow. The term used to describe blood flow is flux – a quantity proportional to the average speed of the blood cells and their concentration. This is expressed in arbitrary perfusion units (PU), which are linearly related to flux. The PeriFlux System 5000 (Laser Doppler Blood Perfusion Monitoring and  $\text{tcpO}_2/\text{tcpCO}_2$ ) along with the Laser Doppler Probes for the PeriFlux System 5000 will be used to perform the LDF technique.

The other secondary outcome will be the time needed to obtain a complete re-epithelialization of the FGG donor site, and will be performed by a non-invasive peroxide test. This test is based on the principle that if the epithelium is discontinuous, the  $\text{H}_2\text{O}_2$  diffuses into the connective tissue; the enzyme catalase acts on  $\text{H}_2\text{O}_2$  to release water and oxygen: this is clinically shown by the production of bubbles on the wound. 3%  $\text{H}_2\text{O}_2$  will be applied to the FGG donor site with a syringe and the appearance of bubbles will be recorded as a dichotomous variable (yes/no) at the post-operative days 3, 7, 14, and 21 until a subject's FGG donor site has

completely epithelialized (no bubbles observed), when they will not be measured again at future post-operative visits.

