#### *Statistical Analysis*

Descriptive statistics will be expressed as means+/- SD and frequency distributions. Intergroup (FFG donor site using episil® and Surgicel® (test) and FGG donor site with PeriAcryl®90 and Surgicel® (control)) comparisons at 1, 2, 3, 5, 7, 10, 14 and 21 days will be analyzed by the Mann-Whitney U test. The Wilcoxon signed-rank test will be used for intragroup comparisons between 1, 2, 3, 5, 7, 10, 14 and 21 days. Differences in frequency distributions between the episil® group and the PeriAcryl®90 group will be analyzed by the Fisher exact test. Associations

between pain VAS scores and the number of analgesic pills or number of days analgesics were taken will be examined by the Pearson correlation coefficient. The significance level for rejection of the null hypothesis will be set at  $\alpha = 0.05$ .

All LDF recordings, which may be impaired by artifacts caused by the relative motion of the probe, will be excluded. An average of the 2-minute period of each individual recording will be calculated. Changes of blood flux values in the FGG donor site will be expressed as the difference ( $\Delta PU$ ) between the PU value at a specific site at a specific observation time point ( $PU_t$ ) and the individual baseline value of the same site ( $PU_0$ ):  $\Delta PU_t - PU_0$ .

Descriptive statistics will be performed using the SPSS statistical software. The  $\Delta PU$  values in the FGG donor site will be analyzed using the general linear model (GLM) univariate test, after verification of the assumptions of homogeneity of variance and normality of the residual distribution. The observation time and point and the position (mesial, center, distal and apical to the FGG donor site) will be modeled as fixed factors and the patient as a random factor with the  $\Delta PU$  as the dependent variable. The Dunnett two-sided *t*-test will be used, in order to evaluate the differences between baseline and subsequent time points and between different positions in the FGG donor site during the overall observational period. Data will be presented as mean SE. Statistical significance will be accepted at  $p < 0.05$ .

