The outcome analysis of the time needed to obtain complete re-epithelialization of the FGG donor site will be made by comparing experimental groups on the frequency distribution of patients experiencing complete re-epithelialization in each of the 4 post-operative visits. The Williams-adjusted log-likelihood ratio was performed, followed by *post-hoc* tests using Bonferroni-corrected Fisher's exact test (2-tailed).

Based on a sample size of  $n = 40$  (20 per group), a repeated measures analysis will have 80% power to detect an effect size of  $f = .57$ . For a sample size of  $n = 30$  (15 per group), the same analysis will have 80% power to detect an effect size of  $f = .67$ , while a sample size of  $n = 20$  (10 per group) will have 80% power to detect an effect size of  $f = .83$ . All of these effect sizes are classified as large effects by Cohen's guidelines (1988), or large differences in the change in pain score between the two groups.

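### The laser Doppler model contains time, position and patient but no treatment arm, so no between-arm test of the blood-flow secondary aim is clearly prespecified

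*Combined protocol and SAP*

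**What the plan says.** Background, Aim, & Hypothesis sets a secondary aim "to compare gingival healing via measurement of the gingival blood flow at the FGG donor sites by the laser Doppler flowmetry (LDF) technique". It does so within a parallel-group comparison of two dressings, and hypothesizes that "patient-based outcomes and gingival blood flow will be more favorable for the FGG donor sites being covered by the test wound dressing material" episil than for those under the control dressing. Both are between-arm statements.

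Statistical Analysis gives LDF its own model, contrasts and significance level. Change from baseline in perfusion units (ΔPU) at the donor site goes into a univariate general linear model with observation time and position as fixed effects: "mesial, center, distal and apical to the FGG donor site) will be modeled as fixed factors and the patient as a random factor". The two-sided Dunnett test is used "in order to evaluate the differences between baseline and subsequent time points and between different positions in the FGG donor site". Neither arm nor arm-by-time is listed.

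The same section opens with a between-group rule: "comparisons at 1, 2, 3, 5, 7, 10, 14 and 21 days will be analyzed by the Mann-Whitney U test". No outcome is named. For the other secondary outcome, the section does state a group comparison: "comparing experimental groups on the frequency distribution of patients experiencing complete re-epithelialization".

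**The concern.** A stated hypothesis should have a test that can support or refute it. The LDF model as written describes how perfusion changes over time and varies across positions. Its output contains no estimate, confidence interval or p-value for episil against PeriAcryl.

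The plan also does not say whether the model is run on all patients together or once per arm. Run together, it ignores the randomized comparison. Run per arm, it invites setting one arm's significance beside the other's, which is not a test of their difference. Unless the plan is amended first, the between-arm LDF test would be chosen with the data in hand, with open choices of PU or ΔPU, which position or average, and which day.

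**Working it through.** **No figure to reproduce.** The sample-size paragraph concerns change in pain score. The documents give no variance, correlation or power for LDF. The structural result below needs none of these; the sizes rest on stated assumptions.

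**Inputs from the documents.** 20 patients per arm; 4 positions; readings at baseline, immediately after harvest, and on days 3, 7, 14 and 21, so 5 ΔPU times, of which 4 follow placement of the dressing.

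**1. Can the written model detect an arm difference?** Write ΔPU = mean + time + position + patient + error, and add a constant δ for one arm. Arm is fixed within patient, so δ is absorbed by the patient term. The time and position tests use within-patient differences, in which δ cancels. In 2,000 simulated trials (20 per arm, 5 times, 4 positions), shifts of 1 and 5 between-patient SDs changed no p-value by more than 2e-14, which is rounding error.

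A shift that starts only at day 3 does move the time test. With patient SD = residual SD = 1 and a 1 SD shift in one arm, rejection rises from about 5% to over 99%. But swapping the arm labels leaves the p-values unchanged, so the result cannot be attributed to either dressing.

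**2. Does the Mann-Whitney rule fill the gap?**

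| | Days |
|---|---|
| Mann-Whitney sentence | 1, 2, 3, 5, 7, 10, 14, 21 |
| Pain and analgesic schedule | 1, 2, 3, 5, 7, 10, 14, 21 |
| LDF after baseline | immediately after harvest, 3, 7, 14, 21 |

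The first two rows are identical; Study Population and Design has patients record pain and "the number of analgesic pills taken each day at 1, 2, 3, 5, 7, 10, 14 and 21 days postoperatively". LDF is not taken on days 1, 2, 5 or 10, and the list omits the post-harvest reading. Pain is the likelier target.

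**3. Running the model once per arm.** With no true arm difference, let each run reach significance with probability q. The chance that exactly one does is 2q(1−q):
- q = 0.2 or 0.8: 2 × 0.2 × 0.8 = 32%
- q = 0.5: 2 × 0.5 × 0.5 = 50%
- q = 0.95: 2 × 0.95 × 0.05 = 9.5%

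**4. What an arm term could detect.** Two-sample t test on the patient mean ΔPU, two-sided 0.05, 80% power (noncentral t, noncentrality d√(n/2)): d = 0.91, 1.06 and 1.32 SD at 20, 15 and 10 per arm.

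**5. Why one test must be named.** Assume between-patient SD 1, visit SD 0.5, residual SD 1, and 4 visits × 4 positions. The variance of a patient mean is 1 + 0.25/4 + 1/16 = 1.125, so its SD is 1.061. A constant difference of 1 is then 1/1.061 = 0.94 SD.

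| True difference, days 3, 7, 14, 21 | Overall arm | Arm × time | Joint arm and arm × time |
|---|---|---|---|
| Constant, 1 SD | 83% | 5% | 59% |
| Crossing: 0.8, 0.3, −0.3, −0.8 | 5% | not computed | 99% |

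Testing each of the four days without adjustment gives at least one false positive in 11% to 16% of null trials (18.5% if the days were independent: 1 − 0.95⁴).

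**6. A caution for the repair.** The four positions read at one visit share any visit-level variation. If arm × time is added with patient as the only random effect, its expected mean square is residual variance + 4 × visit variance, while the pooled error carries only part of that. Simulated type I error (10,000 null trials per setting) at assumed visit-SD/residual-SD ratios of 0, 0.1, 0.25, 0.5 and 1.0 is 4.5%, 5.9%, 8.9%, 21% and 43%. On visit means it stays at 4.5% to 5.4%.

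**The case against.** The strongest reply is that a between-arm test already exists. The Mann-Whitney sentence opens the section, is not labelled as pain, defines its groups by donor-site dressing, and includes every post-operative LDF day. On that reading the linear model is only an added description of time course and position. The reading is possible, which is why the finding is that no test is clearly prespecified, not that none exists. It is weak because the day list is the pain schedule and LDF has its own model and significance statement. Even if accepted, it leaves open PU or ΔPU, how positions are combined and which day decides; 4 positions × 4 days allows up to 16 unadjusted tests.

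Several points about the illustrations stand. That a model without an arm variable ignores arm is true by construction, so the simulation only confirms it. The 32% to 50% range depends on the assumed power, and the plan does not say that p-values will be compared across arms. The type I errors in step 6 belong to a possible repair, not to the plan. The choice of test could still be settled by amendment before analysis. None of this supplies the missing arm comparison.

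**Conclusion.** The concern holds and should be fixed. Followed exactly, the LDF analysis cannot test the blood-flow hypothesis; that follows from the listed factors and contrasts and needs no numerical assumption. It is less certain that no arm test exists anywhere, because the Mann-Whitney sentence is ambiguous, but the schedules point to pain. The power and error-rate figures depend on assumed LDF variances. The consequence is confined to one secondary outcome: the primary pain analysis is untouched.

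**What to change.** **Minimum change:** add arm and arm-by-time to the LDF model, name the deciding test in advance, and state which outcomes the Mann-Whitney sentence covers.

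**Recommended form:**
- Restrict to days 3, 7, 14 and 21. Model ΔPU on arm, time, arm × time and position, with baseline PU as covariate and random effects for patient and patient-by-visit. Averaging the four positions per visit first is a simpler alternative.
- Name one test of the aim: the overall arm effect across days 3 to 21, or, if the arms are expected to cross during healing, the joint test of arm and arm × time. Do not name both.
- Report day-specific arm contrasts with a multiplicity adjustment or as descriptive. Keep the Dunnett time and position tests as descriptive.
- Study Population and Design also reads the "contralateral side of the palate, as a positive control", but the LDF model gives those readings no role. Report them by arm descriptively, or use only the pre-surgery value as a covariate. Same-visit contralateral readings are taken after randomization and could be affected by treatment, so they should not be adjusted for.

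**Cost:** SAP wording and one model run, made before the LDF data are examined by arm. The readings are already scheduled; no added visits, measurements or patients.

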#### *Surgical Procedures & Postoperative Care*

As stated above, periodontal residents under the direct supervision of periodontal faculty will perform the FGG procedure in all subjects. The FGG procedure will be performed following the surgical technique of Sullivan and Atkins or Miller. The donor tissue for the FGG procedure will be retrieved from either the right or left side of the palate. The FGG donor sites will be of a standardized size of 10 mm x 10 mm. As stated above, subjects in the control group will receive a hemostatic gauze, Surgicel®, covered by a cyanoacrylate dressing, PeriAcryl®90, at the donor site while the subjects in the test group will receive the same brand of hemostatic gauze, Surgicel®, but covered with episil®. Subjects in the test group will be given the remainder of the bottle of episil® with instructions for home application up to 3 times daily. Postoperative instructions will include discontinuing tooth brushing and flossing around the surgical site for the first 3 post-operative weeks. Subjects will be provided with a prescription for ibuprofen (600 mg) to take as needed for analgesia, unless contraindicated. Acetaminophen with 30mg of codeine will be prescribed to subjects unable to ingest ibuprofen.

The LDF measurements in the FGG donor site and on the contralateral side of the palate will be recorded in four sites. A clear acrylic stent will be fabricated for each subject from individual subjects' dental casts. Holes will be made in the stent in four locations on each the right and left sides of the palate. One site located centrally, one close to the mesial, one close to the distal and one close to the apical of the FGG donor site and in the same locations on the contralateral side of the palate will be measured at each of the specified postoperative appointments. The LDF measurement will be performed at baseline prior to surgery, immediately after harvesting of the FGG donor site, and on post-operative days 3, 7, 14 and 21. The LDF measurements will be performed with the tip of the fibre optic probe inserted into the holes of the individual acrylic stent. The LDF probe will be placed at a

standardized location perpendicularly to the tissues and at a distance of 0.5 mm from the tissues and will remain motionless during the LDF measurements.

Below is a summary of the timeline of the study:

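### The Dunnett test is assigned to comparisons among four laser Doppler positions without a named reference position, so one run covers only three of the six pairs and which three is left open

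*Combined protocol and SAP*

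**What the plan says.** The laser Doppler paragraphs of the Statistical Analysis section model the change in perfusion units from baseline (delta-PU) at the donor site. Observation time is a factor, and "the position (mesial, center, distal and apical to the FGG donor site) will be modeled as fixed factors", with patient as a random factor. The follow-up is a two-sided Dunnett test, whose purpose is given as: "evaluate the differences between baseline and subsequent time points and between different positions in the FGG donor site during the overall observational period". One procedure therefore serves two questions, one about time and one about position. Significance is accepted at p < 0.05, without saying whether that level applies per comparison or to a family.

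The Surgical Procedures & Postoperative Care section describes the positions: "One site located centrally, one close to the mesial, one close to the distal and one close to the apical" of the donor site. It gives none of them the role of reference. The only laser Doppler site called a control is in Study Population and Design: "the contralateral side of the palate, as a positive control". That site is not a level of the position factor, because the model uses donor-site values only.

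**The concern.** Dunnett's test is a many-to-one procedure: it needs one designated level and compares every other level with it. For time, the plan at least names a comparator. For position it names none, and its stated purpose, differences "between different positions in the FGG donor site during the overall observational period", reads most naturally as a question about all pairs.

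Two analysts could each follow the text faithfully, take different positions as reference, test different pairs and report different significant differences. The choice could also be made after seeing the data. At stake is whether the position result is reproducible and complete. The treatment comparison is not at stake.

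**Working it through.** The plan gives no critical value, number of comparisons or family-wise rate for positions, so there is no figure of its own to reproduce beyond the 0.05 threshold.

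**Inputs.** Four positions, two-sided Dunnett, level 0.05 (all from Statistical Analysis). Assumptions added here: equally precise position means, balanced data and a correct error term.

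**1. Pairs covered.** Four positions give 4 × 3 / 2 = 6 pairs. One Dunnett run tests 4 − 1 = 3 and leaves 6 − 3 = 3 untested.
- Center as reference: tests center–mesial, center–distal and center–apical; omits mesial–distal, mesial–apical and distal–apical.
- Mesial as reference: tests mesial–center, mesial–distal and mesial–apical; omits center–distal, center–apical and distal–apical.

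These two choices share one tested pair, and the same is true of any two references.

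**2. Critical value for one run.** With large error degrees of freedom (df), the two-sided Dunnett value c for three comparisons solves

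∫ φ(x) [Φ(x + c√2) − Φ(x − c√2)]³ dx = 0.95,

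which gives c = 2.349. The family-wise error over the three contrasts is then 5.0% by construction (simulation with 1,000,000 draws: 4.995%).

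**3. All six pairs at that cut-off.** This applies only if the test is rerun with each position as reference. The largest of the six absolute differences is the range of four means, so the cut-off on the range scale is q = 2.349 × √2 = 3.322, and

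family-wise error = 1 − 4 ∫ φ(x) [Φ(x) − Φ(x − q)]³ dx = 8.72%.

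Simulation gives 8.73%. At 60 and 117 error df it gives 8.6% and 8.7%; across all runs with df from 57 to 500 the range is 8.6% to 8.8%. For scale, six unadjusted tests at |t| > 1.96 would give 20.3%.

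**4. A cut-off suited to all pairs.** The Tukey value for four means is 2.569 (large df) and holds 5.0% over the six pairs.

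| Error df | Dunnett, 3 contrasts | Tukey, 6 pairs | Ratio |
|---|---|---|---|
| 57 | 2.41 | 2.65 | 1.10 |
| 117 | 2.38 | 2.61 | 1.10 |
| large | 2.349 | 2.569 | 1.09 |

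The price of covering every pair is therefore a critical value 9 to 10% higher.

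**The case against.** The strongest reply is that this is one missing phrase. The layout has one central and three peripheral sites, so the authors may have meant center versus margins. With that reference fixed beforehand, Dunnett is valid and holds its level. This stands as far as it goes, but nothing in the documents names the center, and the wording about differences between positions does not limit the question to it.

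A reader might infer that the planned position analysis exceeds a 5% error rate. The documents do not support that. The plan does not say the reference will be rotated, a single run holds 5% over its three contrasts, and a further correction across repeated runs would also hold it. Nor is the p < 0.05 threshold described as family-wise; 5% is the level of Dunnett's own procedure.

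A reader might also infer that the spatial pattern of perfusion is the reason for the four-hole stent, which would make this contrast important. The day 3 entry of the study timeline gives repeatable probe positioning as the purpose. No aim, hypothesis or listed outcome concerns differences between positions. They arise only because position is a fixed factor with a planned follow-up test.

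Finally, the contrast does not bear on the trial's main questions. Laser Doppler flow is a secondary outcome, its stated aim is to compare the two dressings, and the model as described contains time, position and patient but no treatment group. This stands too, and it limits the weight of the point.

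**Conclusion.** The concern holds as a minor correction. The plan assigns a many-to-one test to four positions and names no reference, so one run leaves 3 of 6 pairs untested and the set tested is arbitrary. That follows from the text alone and needs no distributional assumption. The 8.7% is conditional: it applies only to an analyst who reruns the test to reach every pair, and it assumes balanced data, equally precise position means and a correct error term. Excluding motion-affected recordings could shift it slightly. The comparison of episil with PeriAcryl is unaffected.

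It would be tempting to conclude that the other half of the sentence, on "differences between baseline and subsequent time points", is sound because baseline is a natural control. The documents do not support that either. The dependent variable is each site's value minus its own baseline, so delta-PU at baseline is zero for every patient and position and has no variance. Kept as a factor level, it conflicts with the homogeneity of variance that the plan says it will verify; left out, Dunnett has no control level. That is a separate defect.

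**What to change.** In the laser Doppler paragraphs of Statistical Analysis, remove positions from the Dunnett sentence and do one of the following:

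- State that all six pairs of positions will be compared with Tukey adjustment from the same model.
- If only center versus margin is of interest, name the central position in advance as the Dunnett reference and limit the claim to those three contrasts.

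Either way this is one sentence, with no new data, visits or subjects. The first option raises the critical value by about 10% and widens the intervals for position differences in proportion. The second keeps the Dunnett cut-off but gives up any statement about the three peripheral pairs. Neither option repairs the comparison with baseline, which should be revised separately.

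### The only power statement is for a repeated-measures analysis of pain that the plan does not contain, so its 80% is not the power of the planned pain comparison

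*Combined protocol and SAP*

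**What the plan says.** **Primary outcome (Study Population and Design).** "The primary outcome of postoperative pain will be determined by the subjects recording their postoperative pain threshold using a Visual Analog Scale Form/Questionnaire", together with the "number of analgesic pills taken each day at 1, 2, 3, 5, 7, 10, 14 and 21 days postoperatively". That is eight pain days.

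**Planned comparisons (Statistical Analysis).** Between-arm "comparisons at 1, 2, 3, 5, 7, 10, 14 and 21 days will be analyzed by the Mann-Whitney U test". Days within an arm are compared by the Wilcoxon signed-rank test, and frequency distributions between arms by Fisher's exact test. "The significance level for rejection of the null hypothesis will be set at" .05. No adjustment across the eight days is given, and the sidedness of the pain tests is not stated. No test is labelled primary. The Mann-Whitney sentence does not name VAS; the link is inferred because its eight days are the pain days.

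**The only model spanning time points (Statistical Analysis).** For the blood-flow change, time and position "will be modeled as fixed factors and the patient as a random factor". Treatment arm is not among the listed factors.

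**Power (end of Statistical Analysis).** "a repeated measures analysis will have 80% power to detect an effect size of" f = .57 at n = 40 (20 per group), .67 at n = 30 and .83 at n = 20. These are described as "large differences in the change in pain score between the two groups".

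**The concern.** A power figure belongs to one test of one quantity. Here the quantity is a between-arm difference in change in pain and the test is a repeated-measures analysis. The analysis plan contains no such test for pain, so the 80% is attached to nothing that will be run.

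The statement is also the only quantitative support for 40 subjects. As written, a reader cannot tell what pain difference the planned tests can detect. With no primary comparison named, the result could be read from any of eight days, or from a repeated-measures model added after the data are seen.

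**Working it through.** **1. Can the stated figures be reproduced?** The plan gives n, f and 80%. It does not give the number of time points m, the within-subject correlation, the handling of sphericity, the convention for f, or whether the effect tested is arm or arm-by-time. Assumptions are therefore needed. Power from the noncentral F at the stated f, for n = 40 / 30 / 20:

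| Assumed setting | Power |
|---|---|
| Arm-by-time, λ = N f², df = m−1 and (m−1)(N−2), m = 6, α = .05 | .793 / .804 / .805 |
| Same df, λ = (N−2) f², m = 5, α = .05 | .801 / .804 / .788 |
| 1-df group comparison, λ = N f², α = .01 | .808 / .809 / .785 |
| 1-df group comparison, λ = N f², α = .05 | .940 / .943 / .939 |

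For n = 40, λ = 40 × .57² = 13.0. Three different settings come within about 2 points of 80% at all three sizes. The figures are plausible for some F test, but the text does not identify which one. A plain one-occasion group comparison at .05 is not among them: it would need only f = .455 / .530 / .662.

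**2. Is the powered analysis in the plan?**

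| | Power statement | Planned for pain | Planned for blood flow |
|---|---|---|---|
| Method | Repeated measures | Mann-Whitney by day; Fisher on frequencies | Linear model over time |
| Outcome | Change in pain score | Pain on each of eight days | Change in perfusion units |
| Between-arm effect | Yes | Yes | No arm term listed |
| Spans time points | Yes | No | Yes |

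No planned analysis matches the first column.

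**3. Power of the test that is written.** Inputs: n per arm 20 / 15 / 10 and the stated f. For two equal groups f = d/2, so d = 2f = 1.14 / 1.34 / 1.66 SD. Assumptions: normal data with a shift, two-sided test. A repeated-measures f need not equal a single-day d/2, so this is illustrative. Simulation with 200,000 replicates; ranges run over the exact test and the normal approximation:

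| Mann-Whitney on one day | n = 40 | n = 30 | n = 20 |
|---|---|---|---|
| Power at α = .05 | 93% | 92-93% | 91-93% |
| Power at α = .05/8 = .00625 | 71-73% | 70-72% | 62-67% |
| f for 80% power, α = .05 | .47 | .54-.55 | .68-.70 |
| f for 80% power, α = .00625 | .61-.62 | .72-.74 | .94-.97 |

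The .00625 rows show what an adjustment would do; the plan contains none for pain.

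With 20 per arm, f = .47 is 2 × .47 = 0.94 SD, and f = .62 is 1.24 SD. An illustrative rounded 0-10 score also gave about 80% at f of about .47. If pill counts were tested on the same eight days there would be 16 tests at .05/16 = .003125. Power at f = .57 would then be about 61-62%, and 80% power would need about 1.33 SD (f about .67).

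**4. What does change refer to?** The timeline chart ticks the VAS row only from the day-3 visit, and the home forms start on day 1, after treatment. No pre-operative score is scheduled, so change in pain score has no defined reference.

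**The case against.** **The harm is small.** For the tests as written, one day at .05 without adjustment, the stated f is conservative. The power paragraph also reports detectable effects at three fixed sample sizes; it does not derive 40 from a target difference. Both points stand. They reduce the matter to a mismatch in the plan, but they do not make the 80% the power of any planned test.

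**No test is called primary, and VAS is not named in the Mann-Whitney sentence.** This is true. Fisher's exact test might also be applied to the three pain categories, which would be a second between-arm comparison of pain. Neither is a repeated-measures analysis of change, so the mismatch remains. The ambiguity is itself a reason to name one comparison.

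**Stronger readings that a reader might infer:**

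- *That the trial is underpowered.* The documents do not support this. The figures below 80% for Mann-Whitney tests require a multiplicity adjustment that the plan does not make for pain.
- *That a repeated-measures analysis over the eight pain days would have only about 74-75% power.* That follows from λ = N f² with m = 8 (.738 / .751 / .753), a convention picked because it fits at m = 6. Under another common convention, with compound symmetry and an assumed correlation ρ from 0 to .9, an arm effect with λ = N f² m / (1 + (m−1)ρ) has about 96% to over 99% power. An arm-by-time effect with λ = N f² m / (1−ρ) has over 99%. The documents do not say which applies.
- *That the power was computed for blood flow*, because six time points fit and blood flow is measured "at baseline prior to surgery, immediately after harvesting of the FGG from donor site, and on post-operative days 3, 7, 14 and 21". Other settings fit as well, and the text speaks of pain. The source cannot be told from the documents.

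**Conclusion.** The power statement and the pain analysis do not match. The first names a repeated-measures analysis of between-arm change in pain, and the second consists of single-day Mann-Whitney tests with Fisher tests on frequencies. This rests on the text alone and needs no calculation.

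The direction of any error in power cannot be stated, because the inputs to the 80% are missing. What can be said is conditional on a normal shift, d = 2f and two-sided testing. With 20 per arm, the f detectable with 80% power is about .47 for one unadjusted day, about .62 for eight adjusted VAS days and about .67 if pill counts join them; the plan states .57. The mismatch does not invalidate the trial, but it concerns the primary outcome and should be corrected.

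**What to change.** In Statistical Analysis, name one primary between-arm VAS comparison, make the other days and the analgesic pill count secondary (unless they are co-primary under option b), and replace the power statement with the one for that test. The options are:

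- **(a) One named day.** VAS pain compared between groups on that day by a Mann-Whitney test at .05. State whether it is two-sided; the plan does not, and two-sided is assumed here. With 20 per group, 80% power at about 0.94 SD (f about .47), assuming a normal shift.
- **(b) All eight VAS days co-primary**, Bonferroni-adjusted at .00625 each, VAS only: about 1.24 SD (f about .62) on the same assumptions. If pill counts are co-primary too, 16 tests at .003125: about 1.33 SD (f about .67).
- **(c) A repeated-measures model, if that was meant.** Add it for pain with arm and arm-by-time terms and say which is primary. Recompute the detectable f for the eight pain days, stating the f convention, the assumed correlation and the sphericity handling.

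In each case, define change in pain score or drop the phrase, since no pre-operative VAS is scheduled.

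The cost is a short edit to one section and a commitment to one primary pain comparison. Enrolment and visits do not change.
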